10.2 Secondary study parameter(s)

Details of secondary analyses will be given in the M-SAP.

10.3 Exploratory parameters

Qualitative data collection and analysis will be done concurrently. Interview data from the three stakeholder groups (researchers, healthcare professionals and patients) will initially be analysed separately from one another, using thematic and framework analysis taking an inductive approach. Nvivo software will be used to assist with the organisation of data. A thematic framework will be used to chart data across all interviews within stakeholder groups and will aid comparisons between participants. Later stages of analysis will compare data across stakeholder groups.

10.4 Interim analysis (if applicable)

The pre-specified design allows adaptations to the trial based on the observed primary endpoint data. These adaptations include the declaration of success or futility of an intervention at an interim analysis and the dropping of treatment arms based on pre-specified decision criteria. The adaptive algorithm will be documented in the M-SAP, including pre-specified criteria for decisions regarding futility or effectiveness of interventions and/or replacing

interventions in the trial. The Simulation Report in the M-SAP will contain extensive simulations to explore the performance of the adaptive design, including power and type 1 error.

The timing of the first interim analysis and frequency of subsequent interim analyses will be pre-specified in in the M-SAP and DSMB charter and will be based on both simulations and logistical considerations.

10.5 Subgroup analysis

We will look at the effect of aetiology on treatment effect by fitting the primary outcome model with an interaction term between aetiology and treatment, where aetiology is split for the most prevalent circulating viruses (2 or 3, and rest) at the time of inclusion.

Additionally, subgroup analyses will be performed by age, comorbidity status and vaccination status.

10.6 Definition of population for analysis

For each intervention, the primary analysis population is defined as participants who were randomised to that intervention or the usual care arm and eligible for randomisation to that intervention, during the same time frame when the intervention was actively randomising (i.e. Concurrent Randomised and Eligible Analysis Population) and have at least one post-baseline measurement.

Primary Analysis Set:

For each IP, all participants randomised to either the IP or its comparator (placebo or usual care and eligible for the IP). Participants later found to be ineligible (randomised in error) will be excluded. Non-concurrent comparators will not be included.

Safety Analysis Set:

All participants who took at least one dose of IP.

Symptomatic Analysis Set:

Primary Analysis Set restricted to those participants who report having the symptom at baseline.

Symptom Free Analysis Set:

Primary Analysis Set restricted to those participants who report not having the symptom at baseline.

Virology Analysis Set:

To be defined

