C. Usual Care + Saline Nasal Spray ((comparator) IP)

Saline is a saltwater solution with possible antiviral and/or virus washing-out activity. Saline will be administered intranasally, six times per day [2 sprays per nostril, equivalent to 0.45 mL volume total per dose (4 sprays)], for seven days.

The additional inclusion criteria for Usual Care and Saline are the same as the additional inclusion criteria for NONS, as Usual Care is the comparator of Saline and Saline is the comparator of NONS.

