8.2 Randomisation, blinding and treatment allocation

8.2.1 Randomisation

With each new IP entering the platform, the randomisation ratio will be adapted. The day of randomisation will be Day 0. Treatment initiation will be as close to Day 0 as possible, using methods that may include directly dispensing IP to participants, or couriering medications to participants who are recruited centrally.

Included patients will be allocated to either an IP arm or a control arm. Each IP has a matching placebo or comparator. For specific IPs Usual Care can be a control arm (specified in ISA). When there is more than one arm with matched placebos in the trial simultaneously, placebos will be pooled for the primary analysis. This means that allocation will be split equally between all active IP arms the participant is eligible for, and placebo. For example, if there are 2 IPs with matching placebo randomisation will be 1:1:1 (Active A):(Active B):(Placebo), and within Placebo allocation will be 1:1 (Placebo A):(Placebo B). Primary analysis for a particular IP will include all participants allocated to placebo who were eligible for the IP and randomised in the same time frame, i.e. concurrent and eligible placebo participants. Potential participants can be included if they are eligible to be randomised to at least one IP. The trial will start with three trial arm 1:1:1.

Participants will be randomised using a rapid, secure, web-based randomisation system using non-deterministic minimisation, with a random element. The minimisation factors will be age (<55/≥55 years), time since onset of symptoms (≤2/>2 days), and country (Belgium/France/Germany/Ireland/Poland/Spain/UK). The randomisation sequence will be saved electronically in a working environment with restricted access.

Participants randomised to a treatment arm will be allocated to an IP pack according to the randomisation number. This individual investigational product pack will be dispensed to participants once they are randomised.

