10. STATISTICAL ANALYSIS

Full details of the statistical analysis will be described in the Master Statistical Analysis Plan (M-SAP). An appendix to the M-SAP titled "Simulation Report" provides simulation results that justify the sample size and design of the study. In addition, the M-SAP will be accompanied by arm-specific appendices to describe any planned deviations from the M-SAP. A broad overview of the design and primary analysis is provided below.

ECRAID-Prime is an adaptive platform trial with early stopping rules for futility or superiority. Comparisons will be based on concurrent and eligible controls only, where control is either a (matched) placebo or comparator, or, if deemed necessary, Usual Care. If there are 2 matched placebos with concurrent randomisation, the primary analysis will pool controls unless it is decided otherwise and specified in the ISA. We may carry out sensitivity analyses with matched controls only included. Early stopping rules will be based on posterior probabilities with thresholds defined using simulations to ensure good trial performance with respect to power and type 1 error.

Each treatment will be analysed separately.

Baseline characteristics will be summarised by IP arm. Continuous variables will be presented as means and standard deviations (or medians and inter-quartile ranges for skewed data). Categorical and binary data will be presented as frequencies and percentages. AEs and SAEs will be summarised by treatment arm.

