10.1 Primary study estimand and parameter(s)

10.1.1 Definition of the primary estimand

Participants aged ≥18 years with at least 2 symptoms suggestive of COVID-19 or COVID-likeillness (one respiratory and one systemic) and meeting the IP eligibility criteria, what is the between group difference, estimated by a hazards ratio, in time to first self-report of feeling recovered (TTR) after treatment with an IP compared with placebo or comparator, regardless of treatment discontinuation for any reason or feeling better before starting the medication, and in conjunction with concomitant medication (including anti-viral medication) as necessary? Participants who die within 28 days from randomisation will be censored at 28 days. TTR is measured by response to the daily diary question "do you feel recovered today from your respiratory infection?", and censored at 28 days after randomisation.

Attributes of estimand:

Population – people in the community aged ≥18 years with at least 2 symptoms suggestive of COVID-19 or COVID-like-illness (one respiratory and one systemic) and meeting the IP eligibility criteria.

Treatment conditions – IP compared with placebo or comparator, regardless of treatment discontinuation for any reason or feeling better before starting the medication, and in conjunction with concomitant medication (including anti-viral medication) as necessary. Participants who die will be given a worst-case value and censored at 28 days.

Outcome variable – time to first self-report of feeling recovered, as measured by response to the daily diary question "do you feel recovered today from your respiratory infection?", censored at 28 days after randomisation.

Handling of intercurrent events – treatment policy strategy applied to study treatment discontinuation, feeling better before starting the medication and use of concomitant medication (including anti-viral medication). Composite strategy applied to death within 28 days of randomisation.

Population level summary measure – hazard ratio.

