10.1.2 Estimator

Analysis will include all eligible randomised participants with at least one follow-up time point (any diary data or information from the 28-day follow-up call) in the group to which they were randomised, regardless of subsequent treatment received. A Bayesian piecewise exponential model with weakly informative priors will be used to estimate the hazard ratio for the time to first self-report of feeling recovered within 28 days of randomisation, adjusting for stratification variables and using all observed data (including data observed after treatment discontinuation and irrespective of use of concomitant medication or feeling better before starting the medication, except for participants who die within 28 days of randomisation who will be censored at day 28.

The primary endpoint is time to recovery, as defined by the first instance that a participant reports this. The primary analysis will be a Bayesian piecewise exponential model with weakly informative priors (specified in the M-SAP), with endpoints regressed on treatment and

stratification covariates. Let θ_j denote the log hazards ratio comparing the hazards of recovery for participants in treatment group *j* versus participants in the comparator arm. We will test the hypothesis that:

 $H_0: \theta_j \leq 0$

 $H_1: \theta_i > 0$

If the Bayesian posterior probability of superiority (a log hazards ratio greater than 0 corresponding to quicker return/recovery) for a treatment versus control is sufficiently large (e.g. >= 0.99), the null hypothesis will be rejected and the intervention will be deemed superior to control. The exact threshold of the superiority decision criterion will be determined a priori via simulation to control the one-sided type 1 error of the study at approximately 0.025, and will be specified in the M-SAP.

We will carry out sensitivity analyses to explore the robustness of inferences from the main estimator to deviations from its underlying modelling assumptions and limitations in the data. This may include fitting an adjusted Cox proportional hazards model. A supplementary analysis using an unadjusted log-rank test may also be performed. All sensitivity and supplementary analyses will be specified in the M-SAP.

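### Section 10.6 of the protocol gives two incompatible definitions of the primary analysis population, and they name different control arms for NONS

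*Protocol*

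**What the plan says.** Section 10.6 of the protocol defines the primary population twice. Its lead sentence takes, for each intervention, "participants who were randomised to that intervention or the usual care arm and eligible for randomisation to that intervention". It adds that randomisation must fall in the period when the intervention was actively randomising, and that there must be at least one post-baseline measurement. The Primary Analysis Set follows directly and takes "all participants randomised to either the IP or its comparator (placebo or usual care and eligible for the IP", closes the bracket, and then excludes participants later found ineligible and non-concurrent comparators.

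Elsewhere the control is described as follows:

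- Synopsis additions, arm C: the extra inclusion criteria are shared, "as Usual Care is the comparator of Saline and Saline is the comparator of NONS".
- Section 10, overview: "control is either a (matched) placebo or comparator, or, if deemed necessary, Usual Care".
- Section 10.1.1, treatment conditions of the estimand: "IP compared with placebo or comparator, regardless of treatment discontinuation for any reason".
- Section 10.1.2: the log hazard ratio sets treatment group j "versus participants in the comparator arm".
- Section 8.2.1: "Primary analysis for a particular IP will include all participants allocated to placebo who were eligible for the IP", randomised in the same time frame.

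The synopsis and section 8.2.3 both state that a comparison with Usual Care alone is not double-blind.

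**The concern.** The two definitions in 10.6 do not select the same control for NONS. The lead sentence covers every intervention and names one control, the usual care arm, with no exception for a placebo, a comparator product or an ISA rule.

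Two things are at stake. First, for a Phase IIb/III type evaluation the primary outcome is the participant's own daily diary answer on feeling recovered. An unblinded control leaves that answer open to expectancy and reporting effects that the blinded Saline arm is there to remove. Second, the question changes. NONS against Usual Care includes whatever the act of spraying or the saline itself contributes, and the synopsis allows that Saline may have antiviral or washing-out activity of its own. NONS against Saline removes that part. A protocol that supports two control arms for one primary test also leaves room to choose between them after data are seen.

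**Working it through.** No arithmetic applies. The protocol states no sample size (section 4.4 leaves it to the ISA), no event count and no power, so there is no figure to reproduce. The check is to apply each rule to the three starting arms, Usual Care, NONS and Saline, which section 8.2.1 allocates 1:1:1.

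**1. NONS under the lead sentence of 10.6.** The population is NONS plus Usual Care: two of the three arms, an open-label contrast, Saline left out.

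**2. NONS under the Primary Analysis Set.** The controlling words are the IP or its comparator. Read with the synopsis ("Usual Care is the comparator of Saline and Saline is the comparator of NONS"), this gives NONS plus Saline: again two of the three arms, but a blinded contrast.

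**3. The bracket in the Primary Analysis Set.** It lists placebo or usual care. The synopsis calls Saline neither of these; it labels it a comparator IP. Read strictly, the bracket does not cover Saline, so the second definition does not wholly repair the first.

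**4. Saline as an IP.** Both rules give Saline plus Usual Care, so there is no conflict for that comparison.

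**5. A later IP with a matching placebo.** The lead sentence again points to Usual Care, whereas 8.2.1 and section 10 call for concurrent, eligible placebo participants, pooled by default. Under 8.2.1 Usual Care is a control only for specific IPs. If no Usual Care arm were active, the lead sentence would define a population with no control group.

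**6. Agreement with the rest of the protocol.** The synopsis, 8.2.1, the section 10 overview, 10.1.1 and 10.1.2 all make the placebo or comparator the reference. Section 10 admits Usual Care only if deemed necessary. The lead sentence of 10.6 is alone in making it the sole control for every intervention.

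**The case against.** The best defence is that one sentence is out of line and the reader can see which. The formally labelled Primary Analysis Set uses the comparator, and the Symptomatic and Symptom Free sets are built from it, so it is arguably the operative definition. Five other places agree with it. The bracket may be loose shorthand: the note to Figure 1 also describes control as Usual Care with or without placebo, although the launch control for NONS is Saline. Section 10 calls itself a broad overview, and the M-SAP and ISAs, which are not shown, may name the right control.

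Much of this stands. A reader might infer that NONS would in fact be tested against Usual Care. The documents do not support that: an analyst would have to override the Primary Analysis Set, the estimand, the estimator and the synopsis to do it. A reader might also want to attach an inflated false-positive rate. That would need an assumed number per arm, proportion recovered and expectancy hazard ratio, none of which the protocol gives. The 0.99 threshold in 10.1.2 is only an example, to be calibrated by simulation to a one-sided error of about 0.025 in a design with interim looks. Such a figure would illustrate open-label bias in general and would not measure this defect.

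The defence does not remove the contradiction. This is a stated rule and not a detail left to the M-SAP. If the M-SAP names Saline, it will conflict with an explicit protocol sentence.

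**Conclusion.** The point holds as an internal contradiction. Section 10.6 contains two incompatible definitions of the primary analysis population. The first, taken literally, replaces the blinded NONS versus Saline contrast with an open-label one and does not estimate the estimand in 10.1.1. The second is right in substance, but its bracket does not name a comparator product.

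In size, the choice of reading swaps the entire control arm for NONS, leaves the Saline versus Usual Care comparison unchanged, and would affect any later IP whose control is a placebo or comparator product. No bias in the hazard ratio and no error rate can be derived from this document. The expectancy argument assumes a Phase IIb/III type evaluation with self-reported recovery as primary outcome; the phase for NONS is left to the ISA. The contradiction itself does not depend on that assumption.

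**What to change.** In the lead sentence of 10.6, replace the words naming the usual care arm with: *or its control as specified in the ISA (matched or pooled concurrent placebo, comparator product, or usual care)*. Keep the existing conditions on concurrency, eligibility and at least one post-baseline measurement. The last of these matches the estimator in 10.1.2, and naming pooled placebo preserves the default in 8.2.1 and section 10. Arm names are best left out, since section 1.4 reserves IP specifics for the appendices.

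In the Primary Analysis Set, make the list of controls in the bracket read: *placebo, comparator product or usual care, as specified in the ISA*. Leave the eligibility condition that follows it in place. The two paragraphs then give one consistent definition, and the M-SAP population should be checked against it.

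The cost is a short wording change in one section. It needs no new data and no change to randomisation or follow-up.

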- Willing and able to give informed consent for participation in the study.

• Willing and able to comply with all trial procedures.

Any additional eligibility criteria relevant to women of child-bearing potential, including current pregnancy and/or breastfeeding will be specified in the ISAs.

Participants who meet any of the following exclusion criteria will be excluded from participation in the trial:

- Requiring admission to the hospital on the day of screening, or inclusion.
- Known allergies or hypersensitivities to any of the components used in the formulation of the IP, or the control product.
- Any disease, condition, or disorder that precludes participation in the trial, in the opinion of the person checking eligibility and taking consent.
- Any planned major surgery in the next 28 days.
- Currently participating in a trial of a pharmacological treatment.

Any additional inclusion and/or exclusion criteria for specific IPs will be detailed in the ISAs.

Interventions

Each IP will have a matching placebo and/or comparator. Usual Care alone can be an additional control arm; only this particular comparison is not double-blind. Participants will be randomised to receive either Usual Care alone, or an IP, a placebo or comparator product in addition to Usual Care. Potential participants can be included if they are eligible for at least one IP, as well as Usual Care.

SYNOPSIS additions for ISA A, ISA B and ISA C

The ECRAID-Prime trial will start with the following three arms:

A. Usual Care (control)

Participants randomised to Usual Care will receive usual clinical primary care according to standard care in the specific country, at the discretion of the responsible treating clinicians.

B. Usual Care + Nitric Oxide Nasal Spray (IP)

Nitric oxide nasal spray (NONS) is a nitric oxide donor that is expected to have an antiviral effect and to accelerate viral clearance in patients infected with SARS-CoV-2 and other respiratory viruses. NONS will be administered intranasally, six times per day [2 sprays per nostril, equivalent to 0.45 mL volume total per dose (4 sprays)], for seven days.

Additional inclusion criteria for NONS are:

- Onset of symptoms within **3 days** of randomisation.
- For women of child-bearing potential: a negative urine pregnancy test.
- For women of child-bearing potential: prepared to use a highly effective method of contraception, or abstinence for a period 30 days before and after terminating study medication intake.

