2.2 Secondary study objectives

The key secondary outcome will be early sustained recovery, which is defined recovery by day 14, sustained until day 28.

Other secondary objectives include assessment of the efficacy and safety of the study IP versus control on:

- Sustained recovery (participants' reported recovery that was maintained until 28 days)
- Time to first self-report of feeling recovered from individual symptoms of COVID-19 or COVID-like-illness (for Phase IIa type evaluation)
- Viral clearance (for Phase IIb and III type evaluation)
- Time to first self-report of return to usual daily activity
- Presence, duration and severity of individual respiratory symptoms
- Participant reported overall wellbeing
- Evaluation of overall safety of the IP by monitoring of (serious) adverse events and (serious) adverse drug reactions
- The use of additional antiviral medication
- The use of other prescribed and/or over-the-counter (OTC) medication for the RTI
- The occurrence of complications (hospitalisation, death; all-cause, non-elective hospitalisation will be assessed)
- Impact on usual daily activities
- Health care utilisation (e.g. general practitioner (GP) and hospital visits)
- Long-term (up to 6 months) consequences of COVID-19 or COVID-like-illness
- The incidence of COVID-19 and COVID-like-illness in other members of the household

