8. METHODS

8.1 Study parameters/ endpoints

- 8.1.1 Primary study endpoints (phase dependent) will be:
- Time to first self-report of feeling recovered from symptoms related to COVID-19 or COVID-like-illness (for Phase IIb/III type evaluation).
- Viral clearance and potentially impact on biomarkers of illness severity (for Phase IIa type evaluation, assessed at baseline and on days 4, 7 and 14 or specified in ISA if samples will be taken on other days).

8.1.2 Secondary study parameters/endpoints include:

Key secondary outcome: early sustained recovery (recovery by day 14 sustained until day 28). Other secondary endpoints:

- Sustained recovery (participants' reported recovery that was maintained until 28 days)

- Time to first self-report of feeling recovered from symptoms of COVID-19 or COVIDlike-illness (for Phase IIa type evaluation)
- Viral clearance (for Phase IIb/III type evaluation, assessed at baseline and on days 4,
 7 and 14 or specified in ISA if samples will be taken on other days).
- Time to first self-report of return to usual daily activity.
- Presence, duration, and severity of individual respiratory symptoms (runny/congested nose, sore throat, cough, fever shortness of breath, fatigue/tiredness, sweats/chills, headache, muscle, joint and/or body aches, loss of taste/smell, diarrhoea, nausea/vomiting, other) as: absent, mild, moderate, severe.
- Participant reported overall wellbeing, reported by rating of how well participant feels (scale 0-10).
- Overall safety of the IP by reporting (serious) adverse drug reactions.
- The use of additional antiviral medication (yes/no, name of medication)
- The use of other prescribed and/or OTC medication for the respiratory infection (antibiotics, antiviral medication, ibuprofen, other pain/fever medication, inhaled medication, intranasal medication, other).
- Impact on usual daily activities (work/education, caring for (grand-) children, household activities, sports, social life), as: no, slight, moderate, severe, not applicable.
- Complications (hospitalisation, death; all-cause, non-elective hospitalisation).
- Health care utilisation for COVID-19 or COVID-like-illness (GP and hospital visits).

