9.2 AEs, SAEs and SUSARs

9.2.1 Adverse events (AEs)

AEs will be recorded for a maximum of 28 days. AEs are defined as any undesirable experience, unrelated to the respiratory infection, occurring to a participant during the study, whether or not considered related to the IP. For each IP/control, all AEs reported by participants in a daily diary from the start of treatment for a 28-day period or during the end-of-treatment telephone call assessment at day 14 (window 14-18 days) after randomisation) will be recorded. AEs will be assessed by a registered/delegated clinician for causality and severity (definitions below).

The participant will be asked to rate the severity of symptoms related to the respiratory infection, which can also be adverse drug reactions (for example headache), in their daily diary. The severity of individual events and symptoms will be assessed over time by participants on the following scale: absent, mild, moderate, severe.

Respiratory symptoms and adverse drug reactions may overlap and can be difficult to disentangle. Trends in the prevalence in the severity of symptoms between control and IP arms will be compared, for evidence of increased severity of measured symptoms in those randomised to receive IPs.

Participants will be free to withdraw from taking the IP/control if they perceive an intolerable AE, unrelated to the respiratory infection. Participants will be provided with a participant card with a telephone number of the coordinating team, enabling them to report issues that are experienced whilst taking the drug. This card will also alert hospital clinicians about trial participation, should a participant be admitted to hospital. In the event of a medical emergency, trial participants will be instructed to show this card to the clinician they see. Based on clinical judgement, the medical monitor/study team may contact the participant to advise the participant on the appropriate clinical care.

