9.2.2 Adverse drug reactions (ADRs)

All adverse events judged by either the investigator/delegate or the Sponsor as having a reasonable suspected causal relationship to an IMP qualify as adverse drug reactions (ADR). An unexpected ADR is an ADR of which the nature or severity, outcome or frequency is not consistent with the applicable reference safety information for the IP.

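### The only defined Safety Analysis Set and the stated safety endpoint both exclude Usual Care, so Saline versus Usual Care has an empty control group in that set

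*Protocol*

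**What the plan says.** Protocol section 10.6 sets the Safety Analysis Set as "All participants who took at least one dose of IP". No other safety population is defined, and there is no rule for participants allocated to no product.

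The safety endpoint in section 8.1.2 reads "Overall safety of the IP by reporting (serious) adverse drug reactions". Section 9.2.2 says which events count: those judged as "having a reasonable suspected causal relationship to an IMP qualify as adverse drug reactions (ADR").

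The secondary objective in section 2.2, which is framed as the study IP versus control, is wider: "Evaluation of overall safety of the IP by monitoring of (serious) adverse events and (serious) adverse drug reactions". Section 9.2.1 describes collection as "For each IP/control, all AEs reported by participants in a daily diary from the start of treatment for a 28-day period", and chapter 10 says AEs and SAEs will be summarised by treatment arm.

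On the arms, the synopsis additions for ISA A, B and C say: "Participants randomised to Usual Care will receive usual clinical primary care according to standard care in the specific country". They also say that "Usual Care is the comparator of Saline and Saline is the comparator of NONS". Section 8.2.1 starts the three arms at 1:1:1.

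**The concern.** A safety comparison needs a control group that can enter the analysis set and can have the event being counted. Usual Care fails on both counts. Membership requires a dose of a product that the arm does not get, and the endpoint requires a causal link to such a product.

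This matters most for Saline, which is under evaluation in its own right and has Usual Care as its comparator. NONS versus Saline cannot show harm from spraying itself, because both arms spray. Usual Care is the only unsprayed arm. If the set and endpoint are carried into the analysis as written, the formal safety tables for Saline will have no control column, although section 2.2 promises one.

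**Working it through.** The protocol gives no figure to reproduce here. The check applies the stated rules to each starting arm.

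**Inputs**
- Entry rule: at least one dose of IP (10.6).
- Arms: Usual Care without product, NONS, Saline (synopsis additions for ISA A, B and C).
- Allocation: 1:1:1 (8.2.1).
- Endpoint: adverse drug reactions (8.1.2), with causality to a medicinal product required (9.2.2).

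**Step 1: who can enter the set**
- Usual Care: no dose is possible, so 0 of 1 allocation share.
- NONS: up to 1 of 1, for those who took at least one dose.
- Saline: up to 1 of 1, because the synopsis labels the arm "C. Usual Care + Saline Nasal Spray ((comparator) IP").

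Maximum share of randomised participants in the set = (0 + 1 + 1) / 3 = 2/3 = 66.7%. Share excluded by definition = 1/3 = 33.3%.

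**Step 2: what each comparison looks like inside the set**
- NONS versus Saline: 1:1, intact.
- Saline versus Usual Care: 1:0, empty control group.

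**Step 3: sensitivity to the meaning of IP**

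Section 9.2.1 names IP and control separately. If IP were read narrowly in 10.6, Saline would also drop out and NONS would lose its control. Usual Care is excluded under either reading.

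**Step 4: whether the endpoint can occur**

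An adverse drug reaction is defined by suspected causality to a product. Without a product, the Usual Care count is 0 whatever happens to the participant.

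**Step 5: the other passages side by side**
- 2.2 promises safety versus control, by AEs and reactions; 8.1.2 keeps only the reactions.
- 9.2.1 records AEs for control as well as IP; 10.6 has no place for those from Usual Care.
- Chapter 10 plans AE and SAE summaries by arm but names no analysis set for them.

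These passages show that a controlled safety comparison was intended. They contradict 10.6 and 8.1.2 and do not repair them.

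**Step 6: the time window**

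Section 9.2.1 counts AEs from the start of treatment, which Usual Care does not have. Randomisation is Day 0 for everyone (8.2.1), product starts on Day 0 or Day 1 (Table 1, footnote 3), and the diary runs for 28 days from randomisation (3.2). The offset is normally about a day, so this is a matter of tidying.

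**Step 7: with the fix**

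With Usual Care included as allocated, the maximum share becomes (1 + 1 + 1) / 3 = 100%, and Saline versus Usual Care becomes 1:1.

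**The case against.** The strongest reply is that the protocol as a whole does provide for safety by arm, outside the Safety Analysis Set. Chapter 10 commits to AE and SAE summaries by treatment arm with no dose condition. The annual report in 9.4 tabulates SAEs per arm. Section 9.2.1 plans to compare symptom severity between control and IP arms, and the diary symptoms in 8.1.2 include nasal symptoms and sore throat, so local harm from spraying is partly covered. Hospitalisation and death form a separate secondary endpoint with no condition on dose or causality. The DSMB sees unblinded safety data. All of this stands, and it limits the point to the definitions.

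Two stronger readings are therefore not supported. A reader might infer that Saline has no safety control at all; the planned summaries and endpoints just listed say otherwise. A reader might also infer that reactions will be compared between Saline and Usual Care and so be biased against the product. The protocol plans no such comparison; 8.1.2 speaks only of reporting reactions.

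A second reply is that the M-SAP and the ISAs, which are not shown, may settle the matter. They may, and secondary analyses are deferred to the M-SAP. But 10.6 does not defer this set. It leaves only the Virology Analysis Set to be defined and fixes the safety set outright. An M-SAP that follows the protocol inherits the empty control group, and one that departs from it contradicts the protocol.

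**Conclusion.** The point holds in a limited form. As written, no Usual Care participant can enter the only defined safety set, and none can have the stated safety event. One third of randomised participants at 1:1:1 are outside the set, and Saline versus Usual Care has no control group in it. This contradicts sections 2.2 and 9.2.1 and the by-arm summary in chapter 10.

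The one-third figure is a share of the analysis set and not of data lost: the diary procedures in 3.2 and 8.3.2 ask for AEs without restriction by arm. NONS versus Saline is unaffected provided that Saline counts as an IP, as the synopsis labels it. Primary efficacy, type 1 error and the stopping rules are not touched. The correction should be made, but the point is not one on which the trial's main conclusions turn.

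The conclusion assumes that the starting three-arm 1:1:1 configuration applies and that no unseen M-SAP or ISA text replaces the definition in 10.6.

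**What to change.** - **10.6:** define the Safety Analysis Set as participants in product arms who took at least one dose of IP or comparator product, plus all randomised Usual Care participants. Naming the comparator product also removes the doubt about Saline.
- **8.1.2:** state the safety endpoint as all AEs and SAEs by arm, regardless of attributed cause, in line with 2.2. List adverse drug reactions descriptively for the product arms.
- **9.2.1 and the analysis:** count AEs from randomisation (Day 0) to day 28 in every arm, matching the existing diary.
- **Table 1:** the (S)AE row refers to the ISA for whether collection is required; confirm that it is for Usual Care.

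The cost is wording in three sections and that check, with no added participants, visits or assessments. There is one small downside. Saline versus Usual Care is not blinded (8.2.3), so differences in self-reported AEs may partly reflect expectation and need cautious interpretation. SAEs, hospitalisation and death should be shown alongside them.
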